33. National Cancer Institute (NCI). Common Terminology Criteria for Adverse Events (CTCAE) version 4. June 2010: U.S. Department of Health and Human Service
34. Altman DG. *Practical Statistics for Medical Research.* Chapman & Hall, London 1999.
35. Bland JM, Altman DG (1986). "Statistical methods for assessing agreement between two methods of clinical measurement" *Lancet.* 327 (8476): 307–10
36. Girden ER. *ANOVA; Repeated Measures.* SAGE Publishing, Inc, California US 2001
37. Anderson TW. *An Introduction to Multivariate Statistical Analysis.* 3rd.Ed. John Wiley & Sons, New Jersey 2003.
38. Agresti A. *Categorical Data Analysis.* John Wiley & Sons, New Jersey 2002.
39. McHugh ML. Interrater reliability: the kappa statistic. *Biochem Med (Zagreb).* 2012 Oct; 22(3): 276–282.

XIV: Amendments

14.1: Study identification

The Study identification has been changed from OTH /Dr; Amd; con – BCAM/ST – IM/1_22 to V1_OTH/DR; AMD – I/2022

14.2: Study administration

The steering committee is specified page 1, point 0 to:

Project Manager: [name] [name]; Norwegian University of Life Sciences / Meddoc AS, [name]

Project Coordinator: [name]. MSc Osteopathy
Chief Executive Officer (CEO) BulbiTech AS Trondheim

Responsible Ophthalmology: [name] [name], MD, Ophthalmologist
Department of Ophthalmology, Oslo University Hospitals / Ullevål Hospital, Oslo

PhD-fellow: [name] [name] MD, Ophthalmologist
Department of Ophthalmology, Oslo University Hospitals / Ullevål Hospital, Oslo

PhD supervisors: [name] and [name] [name]

14.2: Specification of Standard examination

The specification of Standard examination is included in Chapter 1.7, 1.11, 2.3, and 5.2:
The supporting variables will be recorded by the Standard (ST) investigation for DR and AMD.

Test	No of instances	Variable	Unit	Unit description
GAT	1	Pressure	mmHg	2 digits, 1 decimal
iCare	1	Pressure	mmHg	2 digits, 1 decimal
Acuity chart	1	Visual acuity	logMAR	1 digit, 1 decimal
Contrast chart	1	Contrast acuity	Pelli-Robson score	1 digit, 2 decimals
	1	Nasal step		
	1	Temporal wedge		
	1	Partial arcuate (sup)		
	1	Partial arcuate (inf)		
	1	Arcuate (sup)	Present	Boolean (true / false)
	1	Arcuate (inf)		
	1	Altitudinal (inf)		
	1	Altitudinal (sup)		
Visual field	1	Paracentral		
		MD	dB	2 digits, 2 decimals
	54	X coordinate	Degrees	3 digits, 1 decimal
		Y coordinate	Degrees	3 digits, 1 decimal
	1	Threshold sensitivity	dB	2 digits, 2 decimals
	1	Percentile degree	Score 1-5	1 digit
	1	Defuse defect	dB	2 digits, 1 decimal
	1	Local defect	dB	2 digits, 1 decimal
	1	sLV	dB	2 digits, 1 decimal

	1	False positive	Percent (Reliability)	2 digits
	1	False negative	Percent (Reliability)	2 digits
	1	Mean Sensitivity	dB	2 digits, 1 decimal
	1	Reliability factor	Percent (Reliability)	2digits, 1 decimal
OCT RNFL	1	Average thickness	µm	3 decimals
OCT GCL	1	Volume	mm ³	3 decimals
Pupil	1	Diameter change (max-min)	mm	1 digit, 2 decimals

The central variables related to DR and AMD will be “RAPD NDF”, “Seen /unseen “,” Time until the given point is recorded as seen”, “the light in decibel when the point is seen”, X- and Y-coordinates and “Pupil diameter in mm” and “OCT RNFL “.

14.3: Study population

Chapter 3.2.1 is specified as: The study population 1 consists of patients diagnosed with DR of both gender; passed the age of 18 years; without any other eye disease; suffering from other know serious disease but have a health situation in accordance with expectations related to the age.

Chapter 3.2.2 is specified as: The study population 2 consists of patients diagnosed with AMD of both gender; passed the age of 18 years; without any other eye disease; suffering from other know serious disease but have a health situation in accordance with expectations related to the age.

Chapter 3.2.5 is specified as: The study population 3 consists of gender- and age-matched controls to patients in study population 1 or 2; passed the age of 18 years without any eye diseases; not suffering from other know serious disease and have a health situation in accordance with expectations related to the age.

Chapter 3.3 is specified as: No data from possible participants included in the screening phase but not fulfils the inclusion/exclusion criteria will be recorded in the database

Chapter 6.2 is specified with the following new introduction: Both patients and the age- and gender matched controls must have a health situation in accordance with expectations related to the age and not suffering from other know serious disease.

The following additional specification is done in *Chapter 6.2*: No data from possible participants included in the screening phase but not fulfils the inclusion/exclusion criteria will be recorded in the study database.

Chapter 5.2. The following information is added under 5.2.1: The Quality-of-Life (QoL) questionnaires EQ-5D-5L developed by EuroQol will be recorded once in the study and at the same day as the first BCAM registration. This will be performing as additional health verification and the possibility of comparing QoL of patients and controls.

14.4: Recruitment of patients

Chapter 3.3 is rewritten and no given as follows:

The patients will be recruited from Oslo University hospital, Ullevål and Helgeland hospital. If necessary, private Ophthalmology clinics in Oslo will be asked for recruitment. All the investigations in the study will be performed by the same Ophthalmologist at the given hospital. The investigator informs the patients about the study, handing and collecting the written informed consent form. In case the patient fulfils the inclusion/exclusion criteria and willing to sign the consent form, the patient is included in the study. No data from possible participants included in the screening phase but not fulfils the inclusion/exclusion criteria will be recorded in the database. The included patient will be asked if he/she know any person with same gender and age; in good health condition without any eye disease which may participate as a control in the study. The potential controls will be contacted by the responsible investigator, obtain information about the study, and expected tasks. Controls willing to sign the consent form is included in the study. In case of lack in controls, requests among the hospital staff will be performed.

14.5: Patient factor

The following paragraph are added to *chapter 5.5*: Age and gender will be used to recruit controls to the included patients. Concomitant diseases and medication together with history of disease will be used to demonstrate the health condition of the participants at the time of inclusion in the study. Additionally, quality of life of the participants will be recorded at screening. This will also be a part of the health evaluation but also gives the possibility of comparing the patients with the age- and gender matched controls.

14.6: Data Management

Additions to *Chapter 4.3*. All information in the database will be anonymized and the activation key is stored by the clinically responsible ophthalmologist.

Addition to *Chapter 8.1*. The identity of the participants in the database will be anonymized. The activation key is stored and only to be used by the clinically responsible ophthalmologist. Each study participants are given a study identification number which will be stored in the database

14.7: Ethical consideration

The previous statement under *Chapter 10.1*, page 34:” *No results from previous studies with this new equipment indicate any negative effect on the participants and AE has so far never been reported*” has been removed and replaced by “Despite that BulbiCam not previously has been used in any clinical study, it is nothing that may indicate that BulbiCam causes any adverse events.

The following specification is made in *Chapter 10.1*. All information in the database will be anonymized and the activation key is stored by the clinically responsible ophthalmologist

XV: Appendix**15.1: Set of CRF's***15.1.1: CRF I; Inclusion and exclusion***Case Record Form I (A=DR)**
(Inclusion and Exclusion criteria)

Study Id: V1_OTH /DR; AMD – I/2022; *Participant Initials:* _____*Participant category.* DR patient ; AMD patient ; Healthy Control without any ophthalmological or neurological disease

Inclusion criteria

- | | | |
|---|-------------------------------|--|
| A | Diagnosed with DR |  Yes  No |
| B | At least age of 18 years |  Yes  No |
| C | Without any other eye disease |  Yes  No |
-

Exclusion criteria

- | | | |
|----|--|--|
| 1 | Other visual disturbances and blindness |  Yes  No |
| 2 | Posterior Chamber Artificial Ocular Lens (PCIOL) |  Yes  No |
| 3 | Physical or psychiatric disease disturbing the measuring procedure |  Yes  No |
| 4 | Not able to perform full eye movements |  Yes  No |
| 5 | Visual acuity is less than 1 logMAR in any eye |  Yes  No |
| 6 | Visible part of the eye is abnormal. Haemorrhages/deformed pupils |  Yes  No |
| 7 | Pupils not able to respond normally to dilation or contraction |  Yes  No |
| 8 | Participating another clinical trial with pharmaceuticals |  Yes  No |
| 9 | Not able to understand information |  Yes  No |
| 10 | With known alcoholic and drug dependency |  Yes  No |
| 11 | Not willing to give written consent to participate in the study |  Yes  No |
-

. Has the participant given written consent to participate? Yes No; Date: _____
Investigator (Sign)Date:

Case Record Form I (B=AMD)
(Inclusion and Exclusion criteria)

Study Id: V1_OTH /DR; AMD – I/2022; *Participant Initials:* _____

Participant category. DR patient ; AMD patient ; Healthy Control without any ophthalmological or neurological disease

Inclusion criteria

- | | | |
|---|-------------------------------|--|
| A | Diagnosed with AMD |  Yes  No |
| B | At least age of 18 years |  Yes  No |
| C | Without any other eye disease |  Yes  No |
-

Exclusion criteria

- | | | |
|----|--|--|
| 1 | Other visual disturbances and blindness |  Yes  No |
| 2 | Posterior Chamber Artificial Ocular Lens (PCIOL) |  Yes  No |
| 3 | Physical or psychiatric disease disturbing the measuring procedure |  Yes  No |
| 4 | Not able to perform full eye movements |  Yes  No |
| 5 | Visual acuity is less than 1 logMAR in any eye |  Yes  No |
| 6 | Visible part of the eye is abnormal. Haemorrhages/deformed pupils |  Yes  No |
| 7 | Pupils not able to respond normally to dilation or contraction |  Yes  No |
| 8 | Participating another clinical trial with pharmaceuticals |  Yes  No |
| 9 | Not able to understand information |  Yes  No |
| 10 | With known alcoholic and drug dependency |  Yes  No |
| 11 | Not willing to give written consent to participate in the study |  Yes  No |
-

Has the participant given written consent to participate? Yes No; Date:

Investigator (Sign)

Date:

15.1.2: CRF II; Demographic factors

Case Record Form II (Demographic factors)

Study Id: VI_OTH/DR; AMD-I/2022 [Transferred from the system]

Country: (Norway=1; India=2 etc); Site: (First site =1 Second=2 etc); Disease (None =0;

Glaucoma=1; Cataract=2; DR =3 etc); Disease degree (None=0; Mild =1; Moderate =2; Severe=3);

Running number: *[Created from the system within the group defined by information above]*

Participant Id-number: _ *[Created from the system by using information above]*

Patient initials _____; Date of inclusion:

Demographic factors

Date of birth: Age: (years), Gender: (Male=M; Female=F)

Comment:

Investigator (Sign)

Date:

15.1.3: CRF III; Medical history

Case Record Form III (A=DR)
(Medical history)

Study Id: V1_OTH/DR; AMD-I/2022 [Transferred from the system]

Participant Id-number: □□□□_□□ [Transferred from CRF I]

Actual disease

Specification: DR; Date first time diagnosed: □□ □□ □□

Degree (classification) of disease: □ [specification for each study]

Ongoing treatment

..... Date of start: □□ □□□□
..... Date of start: □□ □□□□
..... Date of start: □□ □□□□
..... Date of start: □□ □□□□

Ongoing concomitant disease

Medical area: Cardiac, Congenital, Ear and Labyrinth, Endocrine, Eye,
 Gastrointestinal, General disorders, Hepatobiliary, Immune system disorder
 Infections, Injury and procedural, Investigations, Metabolism and nutrition,
 Musculoskeletal, Neoplasm, Neurology, Ophthalmology, Pregnancy and perinatal,
 Psychiatric, Renal and urinary, Reproductive, Respiratory, Rheumatic, Skin,
 Social circumstances, Surgical and Medical, Vascular

Ongoing concomitant diagnoses

.....
.....
.....
.....
.....
.....

Ongoing concomitant treatment

..... Date of start: □□ □□□□
..... Date of start: □□ □□□□
..... Date of start: □□ □□□□
..... Date of start: □□ □□□□
..... Date of start: □□ □□□□
..... Date of start: □□ □□□□

..... Date: □□ □□ □□

Investigator (Sign)

Case Record Form III (B=AMD)
(Medical history)

Study Id: V1_OTH /DR; AMD – I/2022 *[Transferred from the system]*

Participant Id-number: □□□□_□□ *[Transferred from CRF I]*

Actual disease

Specification: AMD; Date first time diagnosed: □□ □□ □□

Degree (classification) of disease: □ *[specification for each study]*

Ongoing treatment

..... Date of start: □□ □□□□
..... Date of start: □□ □□□□
..... Date of start: □□ □□□□
..... Date of start: □□ □□□□

Ongoing concomitant disease

Medical area: Cardiac, Congenital, Ear and Labyrinth, Endocrine, Eye,
 Gastrointestinal, General disorders, Hepatobiliary, Immune system disorder
 Infections, Injury and procedural, Investigations, Metabolism and nutrition,
 Musculoskeletal, Neoplasm, Neurology, Ophthalmology, Pregnancy and perinatal,
 Psychiatric, Renal and urinary, Reproductive, Respiratory, Rheumatic, Skin,
 Social circumstances, Surgical and Medical, Vascular

Ongoing concomitant diagnoses

.....
.....
.....
.....
.....
.....

Ongoing concomitant treatment

..... Date of start: □□ □□□□
..... Date of start: □□ □□□□
..... Date of start: □□ □□□□
..... Date of start: □□ □□□□
..... Date of start: □□ □□□□
..... Date of start: □□ □□□□

Investigator (Sign) _____ Date: □□ □□ □□

15.1.4: CRF IV; Quality of life

Case Record Form IV (Quality of Life)

Study Id: V1_OTH /DR; AMD – IM/1_22 [Transferred from the system]

Participant Id-number: □□□□_□□ [Transferred from CRF I]

EQ-5D-5L

BEVEGELSE

- Jeg har ingen problemer med å gå rundt (1)
 Jeg har noen problemer med å gå rundt (2)
 Jeg har moderate problemer med å gå rundt (3)
 Jeg har store problemer med å gå rundt (4)
 Jeg klarer ikke å gå rundt (5)

SELVPLEIE

- Jeg har ingen problemer med å vaske eller kle på meg (1)
 Jeg har noen problemer med å vaske eller kle på meg (2)
 Jeg har moderate problemer med å vaske eller kle på meg (3)
 Jeg har store problemer med å vaske eller kle på meg (4)
 Jeg klarer ikke å vaske eller kle på meg (5)

VANLIGE AKTIVITETER (f.eks. arbeid, studier, husarbeid og familie- eller fritidsaktiviteter)

- Jeg har ingen problemer med å gjøre de vanlige aktivitetene mine (1)
 Jeg har noen problemer med å gjøre de vanlige aktivitetene mine (2)
 Jeg har moderate problemer med å gjøre de vanlige aktivitetene mine (3)
 Jeg har store problemer med å gjøre de vanlige aktivitetene mine (4)
 Jeg klarer ikke å gjøre de vanlige aktivitetene mine (5)

SMERTER / UBEHAG

- Jeg har ingen smerter eller ubehag (1)
 Jeg har noen smerter eller ubehag (2)
 Jeg har moderate smerter eller ubehag (3)
 Jeg har store smerter eller ubehag (4)
 Jeg har ekstrem smerte eller ubehag (5)

[figure not shown]
ANGST / DEPRESSJON

- Jeg er ikke engstelig eller deprimert (1)
 Jeg er noe engstelig eller deprimert (2)
 Jeg er engstelig eller deprimert (3)
 Jeg er veldig engstelig eller deprimert (4)
 Jeg er ekstremt engstelig eller deprimert (5)

EQ-Visual Analogue Scale (VAS)

Pasienten skal beskrive sin daglige helsesituasjon på en 100mm VAS ved å avsette en horisontal strek på skalaen nedenfor hvorav «0» angir «Den verste helsen du kan forestille deg» og «100» angir «Den beste helsen du kan forestille deg»

Angi resultatet i mm fra bunnen og opp til merket på skalaen nedenfor: mm

15.1.6: CRF VI; Adverse Events

Case Record Form VI

(Initial registration by ST)

Study Id: V1_OTH /DR; AMD-I/2022 [*Transferred from the system*]*Participant Id-number:* □□□□_□□ [*Transferred from CRF I*]

The Standard method*GAT-pressure:* □□,□ mmHg*iCare-pressure:* □□,□ mmHg*Acuity chart:* □,□ mmHg*Contrast chart:* □,□□ mmHg*Visible Field*Point seen: Yes NoNasal step: Yes NoTemporal wedge: Yes NoPartial arcuate (sup): Yes NoPartial arcuate (inf): Yes NoArcuate (sup): Yes NoArcuate (inf): Yes NoAltitudinal (inf): Yes NoAltitudinal (sup): Yes NoParacentral: Yes No

MD: □□□,□ dB

X-coordinate □□,□□ degree

Y-coordinate □□,□□ degree

Threshold sensitivity □□,□ dB

Percentile degree Score (1 – 5)

Defuse defect □□,□dB

Local defect □□,□dB

sLV □□,□dB

False positive □□ % (Reliability)

False negative □□ % (Reliability)

Mean Sensitivity □□,□dB

OCT RNFL: □□□ μm*OCT GCL:* □□□ m³*Pupil diameter size:* Min □□□ mm Max □□□ mm**Date:** _____ **Investigator's signature:** _____

15.1.7: CRF VII; End of Trial

Case Record Form VII (End of Trial)

Study Id: V1_OTH /DR; AMD-I/2022 *[Transferred from the system]*

Participant Id-number: □□□□_□□ *[Transferred from CRF I]*

Please state the trial end reason:

- Completion of trial**
 Withdrawal: patient withdrew consent.

Date withdrawal (dd-mm-yyyy): _____

Reason withdrawal:

Adverse experience – please specify: _____

Inter-current illness (must be reported as an AE)

Protocol Violation- please specify: _____

- Drop-out:** patient request.

Date drop-out (dd-mm-yyyy): _____

- Patient lost to follow up.**

Date last contact (dd-mm-yyyy): _____

- Death** – must be reported as a SAE.

Date of death (dd-mm-yyyy): _____

- Other**, please specify: _____

Date of discontinuation (dd-mm-yyyy): _____

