8.2. Study Database

The validated data management system InCRF will be used for collecting the CRF data. The system selected is compliant with GCP guidelines and subject to 21 CFR (Code of federal regulations) FDA part 11 requirements. The final database will be stored in the Statistical Analysis system (SAS ver. 9.4 or later).

8.3: Data handling

A data entry person at site will enter the e-CRF data in InCRF and the DM will perform the initial data validation. In case of missing data, logical errors or interpretation problems, a query will be generated directly in InCRF. Investigator can review the query status via either InCRF function of “Study reports” /” Query report” or patient’s e-Form dashboard. When all the needed participants have finalized the clinical part, and the investigator has electronically signed the e-CRFs, the DM will do the final verification checks and perform final database hard-lock when all errors are corrected.

Screening analysis for logical errors will be evenly performed on this database and errors will be corrected after new information is collected from the site. When all the detected errors are corrected, the main basic database will be locked. The database will be transformed to a labeled SAS database, which also will be locked up to prevent all possible changes or additions. In this copy, the responsible statistician can make derivations but no corrections of the data. If corrections are needed, the main basic study database has to be re-opened and corrected. The international procedure for such changes will be followed.

IX: Discontinuation

A patient may discontinue the study at any time if, in the view of the investigator, it is in the participant's best interests. Alternatively, the participant has the right to discontinue her/his consent and exit the study without prejudice concerning her/his future treatment or care.

If a participant does not show up to an agreed visit, the investigator should try to motivate her/him to continue. However, if the participant has decided not to continue, she/he should be asked to attend a control visit as described for the end of the study (CRF VI).

9.1: Discontinuation not related to the study question

A participant who discontinues the study for administrative reasons or reasons documented not related to the trial equipment classifies as "Drop out" and has to be replaced by a new participant. Such participants will not be included in the statistical analysis.

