9.2: Discontinuation related to the study question

Participants discontinue the study for the reasons are related to or might be related to the trial equipment will be classified as "Patient Withdrawal". These participants will not be replaced. They will be included in the Per-Protocol (PP) and the ITT analysis using the "Last-observation-carried-forward" (LOCF) procedure.

X: Ethical consideration

10.1: Consideration of steering committee

The study will be conducted in compliance with the protocol and according to the Helsinki declaration with latest amendments and Good Clinical Practice (GCP).

Participants will only be included in this clinical trial after approval of the trial by the regional Ethical Committee (REK). The patients will receive oral and written information and have to give signed informed consent for participation.

All participants invited to participate in a clinical trial are entitled to make their decision based on the fullest amount of information available at that time. In order to make the choice, they will be given a written document expressed in a clear concise language of their native tongue to consider.

The document will tell potential participants about the nature of the measurements and the equipment. No interventions; only twice BCAM registration per day consecutively in three days. It will outline the numbers of participants in the trial, the steps of the protocol and type of measurements. This will give the participants a clear picture of the risks, inconveniences, and benefits that may accrue from the trial. The participants will be informed that she/he may decline the offer to join the trial or may withdraw at any time without prejudicing further medical care and is covered by the Sponsor's indemnity insurance in the event of mishap. Individuals must also know that their personal hospital records may be reviewed in confidence by the trial appointed research staff and that all personal information will be held on a confidential database. All information in the database will be anonymized and the activation key is stored by the clinically responsible ophthalmologist. Consent must always be given in writing after the participant has had time to reflect on the information and had an opportunity to ask further questions.

BCAM is new equipment, but certificated for clinical use [ISO 13485:2016] and sale in Norway (Appendix 15.2)

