BCAM may increase the possibility for the investigator to give a safe diagnose at an early stage; give the final diagnose earlier and follow-up the patients more closely during treatment. However, before using such equipment in clinical practice the validity of the measurements must be documented.

Summary: No results from previous studies with this new equipment indicate any negative effect on the participants and AE has so far never been reported. All participants will be given oral and written information and have to give their written consent to participate in the study. To the best of our knowledge, this study fulfils the entire international requirement to an ethical controlled clinical trial.

10.2: Approval of the project

This study will be performed in Norway and the study protocol together and other requested information will be sent for approval by REK. Inclusion of patients will not be started before the approval is received.

The database and storage will be in Norway and must be approved by the Norwegian center for research data (NSD)

10.3: Informed consent

Before the start of the trial, the investigator will explain the confidentiality of participation in this research project; the objectives of the trial; the specific requirements for the participating patients; the trial design and the consequences of participation. Additionally, the investigators have to obtain written informed consent from the participants before inclusion in the study.

10.4: Protection of personal data

The monitor may know the identity of the patients during verification of the source data.

However, the monitor has unconditional professional secrecy.

All patient-related material leaving the department will be anonymous so that the patient only can be identified by date of birth, initials, and study number.

The investigator is responsible for keeping a list with the full names of the patients, their citizens' number, and corresponding study numbers according to the demands in GCP.

XI: Statistical model

11.1: Handling of discontinuation

All patients fulfilling the inclusion and exclusion criteria, given informed consent to participate and started BCAM registration are classified as included in the study. In the ITT analysis, all these patients will be included and if necessary, the LOCF procedure will be used. The patients classified as Drop-out will be excluded from the statistical analysis.

11.2: Presentation of the result

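### CRF VII and Section IX define Drop-out and Withdrawal by different rules, although that class decides who is replaced and who is analysed

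*Protocol*

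**What the plan says.** Section IX of the protocol has two classes, separated by whether the reason for stopping relates to the device.

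- **9.1, Drop-out.** "A participant who discontinues the study for administrative reasons or reasons documented not related to the trial equipment classifies as" a Drop-out. Such a person "has to be replaced by a new participant", and "Such participants will not be included in the statistical analysis". Section 11.1 repeats the exclusion: "The patients classified as Drop-out will be excluded from the statistical analysis".
- **9.2, Patient Withdrawal.** "Participants discontinue the study for the reasons are related to or might be related to the trial equipment will be classified as" a Patient Withdrawal. "These participants will not be replaced", and they stay in the PP and ITT analyses with LOCF.

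The end-of-trial form (15.1.7, CRF VII) uses the same two labels. Its Withdrawal box is for consent withdrawn. The reasons beneath it are an adverse experience, a protocol violation, and the line beginning "Inter-current illness (must be reported as an AE". Its Drop-out box is for a stop at the patient's request and asks for a date only. Loss to follow-up, death and a free-text Other are separate boxes. No item asks whether the stop had to do with the equipment.

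**The concern.** The class does more than label a participant. It settles whether someone is replaced and whether their data are analysed. A participant who stops because of the BulbiCam sessions is the person 9.2 is meant to keep. If that person is filed as a Drop-out, a new participant takes the place and the device-related stop leaves the analysed set. Repeatability and stability come first among the aims (1.3, 2.4), and tolerability is recorded at the end of each day, so selection of this kind would touch the main results. The opposite misfiling is also possible: an unrelated illness filed as a Withdrawal stays in with values carried forward, where 9.1 calls for replacement and exclusion.

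**Working it through.** The point rests on comparing the two sets of definitions. The only arithmetic is the weight of one case.

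**Step 1. The rules side by side**

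| Item | Section IX | CRF VII |
|---|---|---|
| What separates the classes | Relation to the equipment | Manner of leaving |
| Drop-out | Administrative, or documented as unrelated | Patient asks to stop; date only |
| Withdrawal | Related or possibly related | Consent withdrawn, with adverse experience, inter-current illness or protocol violation as reasons |
| Lost to follow-up, death, other | Assigned by relation to the equipment | Separate boxes, in neither class |
| Relatedness recorded | Needed in order to classify | Not asked |

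**Step 2. Cases traced through the form, if its tick sets the class**

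- *A participant asks to stop because of the sessions and is ticked as a Drop-out at patient request.* Form: replaced and excluded. Section 9.2: not replaced and kept. The two disagree.
- *A participant stops for an illness unrelated to the device and is ticked as a Withdrawal for inter-current illness.* Form: kept with LOCF and not replaced. Section 9.1: replaced and excluded. The two disagree.
- *A participant is lost to follow-up.* Form: no class. Section IX needs one, and the form collects only a date of last contact.

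**Step 3. Can the form show that 9.1 is met?** Apart from administrative reasons, 9.1 needs "reasons documented not related to the trial equipment classifies as" a Drop-out. The Drop-out box on CRF VII has no reason line, so it cannot hold that documentation. Under 8.3 the statistician may derive variables from the locked data but not correct them. A reason that was never collected cannot be derived.

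**Step 4. Weight of one case.** Section 11.3 gives 16 patients per diagnosis, and 1.9 gives the matching total of 16 × 2 = 32. One misfiled participant is therefore 1/16 = 6.25% of a diagnosis group. The protocol states no discontinuation rate, so the number of such cases cannot be projected.

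**The case against.** **The form does not force the error.** Consent withdrawn and a stop at the patient's request overlap. A participant who finds the test tiring could be entered under Withdrawal as an adverse experience, since Section 5.2.2.3 defines adverse events broadly, or under Other. This stands: the form permits the misfiling but does not direct it.

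**Nothing says the CRF VII tick fixes the class.** Section IX states the rule, and 11.1 refers only to those classified as Drop-outs. A request with no recorded reason does not clearly satisfy 9.1. This also stands, so the consequence is conditional. Yet the protocol names no other form or step that assigns the class.

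**Relatedness may be captured elsewhere.** Adverse events carry a relationship judgement (5.2.2.1) and an attribution to the study intervention (6.6). Section 8.1 provides for a data entry instruction, and 8.3 for queries. CRF V, the adverse event form, could not be examined. These routes may rescue stops linked to an adverse event. They do not clearly cover a patient-request stop with no adverse event.

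**Stronger readings that the documents do not support.**

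- *A reader might infer that two such cases would lift apparent completion from 14/16 (87.5%) to 16/16.* With two replacements, 18 people have entered and 16 have completed, and 16/18 = 88.9%. The figure of 100% appears only if the Drop-outs are left out of the denominator, which the protocol does not say.
- *A reader might infer a bias in the device's favour overall.* That is plausible when device-related stops are replaced. It is not shown for unrelated illness kept with LOCF, so no overall direction is established.
- *A reader might take inter-current illness and protocol violation to be unrelated to the device.* The protocol does not say so. The defect is that the form lists them under Withdrawal without asking.

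**Conclusion.** The contradiction is real. The same two labels follow different rules in the protocol body and on the form, and the label governs replacement and analysis. CRF VII cannot document the non-relatedness that 9.1 requires, and it leaves three kinds of ending in neither class. If the form is used to classify, errors are possible in both directions, each worth 6.25% of a diagnosis group of 16. How many would occur is unknown. Participation lasts three days with two 15-minute registrations a day, so few are likely. The conclusion assumes that no step outside the protocol, such as the data entry instruction, already maps end reasons to Section IX. It does not show that misclassification will happen, how far it would move any estimate, or in which direction overall. It is worth correcting because the reason cannot be derived later if it was never collected.

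**What to change.** On CRF VII, for every category other than completion, add a reason field and one question: Related or possibly related to BCAM: Yes / No / Unknown. Derive the Section IX class from the answer:

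- Administrative reason, or No with the reason documented: Drop-out under 9.1.
- Yes: Patient Withdrawal under 9.2.
- Unknown: treated as possibly related under 9.2, so not replaced and kept in the analysis, because 9.1 requires an administrative reason or documented non-relatedness.

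State in Section IX that this derivation, and not the heading ticked on the form, sets the class. Report all discontinuations by reason and group, including Drop-outs who were replaced.

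Also reconcile the form number. Sections 6.4 and IX call the end-of-trial form CRF VI, while the appendix makes it CRF VII and uses CRF VI for the Standard Method record.

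The cost is a one-page form change, one sentence in Section IX and a short derivation rule. No procedure for participants changes. The change should be made before the form is used, or the missing reasons obtained by query before database lock.
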